Power Analysis: The power analysis is informed by the ICIQ-OAB symptom score reduction observed in the BETTUR PD and BETTUR2 studies of behavioral therapy for urinary symptoms in PD. Based upon the bladder diary-derived UI frequency data (consistent measure used in both behavioral and drug trials), the effect of behavioral therapy and drug therapy to reduce UI frequency is similar. The ICIQ-OAB symptom score range is 0-16, with higher scores indicating worse symptoms. A score \geq 7 would indicate clinically significant OAB symptoms (urgency, frequency, urgency UI, nocturia) occurring on average at least *sometimes*. In our previous studies, we have observed a 2-3 point reduction in the symptom score, which represents a 12%-19% reduction from baseline^{24,64}. The minimally clinically important difference for the ICIQ-OAB is defined as a statistically significant reduction in the symptom score that is accompanied by a reduction in bother and improvement in OAB-specific QOL. Because the observed reduction **\geq 2 points** represents a statistically and clinically meaningful difference, we propose a non-inferiority margin of 15%. Thus, we will randomize 90 participants in order to complete the interventions in 80 participants, which assumes 85% power and a non-inferiority margin on the OAB symptom score of 15% at 12-weeks post-randomization. **Table 6 indicates that the proposed sample size will permit an assessment of non-inferiority within a range of potential non-inferiority margins that correspond to outcome assessments in our pilot studies.**

Standard Deviation of 12 week ICIQ-OAB Symptom Score	Margin of Non-Inferiority Between Groups at 12 weeks (Assumes OAB Symptom Score at baseline of = 8.1)				
	10%	12.5%	15%	20%	
	1.0	23	16	11	7
2.0	89	59	40	24	
3.0	198	131	88	52	

Table 7: Summary Outcome Assessments

Outcome Assessment	Baseline Visit 1/Visit 2	2 weeks Visit 3	4 weeks Visit 4	6 weeks Visit 5	8 weeks Visit 6	12 weeks Visit 7
ICIQ-OAB	X			X		X
7-day Bladder Diary (drug)	X			X		X
7-day Bladder Diary (behavioral)	X	X		X		X
7-day PFME Record (behavioral)		X				
ICIQ-OAB QOL	X			X		X
Benefit & Satisfaction				X		X
Life Space Assessment	X			X		X
Self Efficacy for Chronic Disease Management	X					X
Patient Global Symptom Control Score				X		X
Adverse Event checklist	X	X	X	X	X	X
Adherence Questionnaire		X		X		X
Neuropsychological battery	X					X
MDS-UPDRS	X					X

Data Analysis:

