Primary Outcome for Aim 1: To evaluate the impact of treatment within group, we will first use a random effects mixed model with adjustment for baseline OAB symptom severity to compare mean ICIQ-OAB symptom scores across the three time points. In order to test for non-inferiority of behavioral therapy compared to drug therapy, we will assess the difference in the mean 12-week post-randomization ICIQ-OAB symptom score between groups using a two-sample t-test, assuming a non-inferiority margin of 15% and a standard deviation of 2.0 points. The significance level of the test will be set at an α of 0.025 for a one-sided test of significance.

Secondary Outcomes: The pre-treatment and post-treatment frequency of UI based on the bladder diary will be used to calculate a percentage change for each participant ($[\text{pre-treatment frequency} - \text{post-treatment frequency}] / [\text{pre-treatment frequency}] \times 100\%$). Based on pilot study results, non-normality of the diary data is anticipated and thus the Wilcoxon rank sum test will be used for bladder diary-reported outcomes (UI, urgency, nocturia). Questionnaire-based secondary outcomes (ICIQ-OAB bother score, ICIQ-QOL, benefit and satisfaction, self-efficacy, voided volume, and the Life Space Assessment) will be assessed between groups using a t-test. Twenty-four hour voided volume measures will permit an evaluation of nocturnal urine production as a confounding factor for response to treatment among persons with nocturia. Nocturnal urine production includes the sum of all voided volumes after going to bed with the intention of sleeping and the subsequent first voided volume the next morning. Additionally, an evaluation of change in mean voided volume provides an objective measure of functional bladder capacity.

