The sample size is informed by the ICIQ-OAB symptom score reduction observed in the BETTUR PD and BETTUR2 studies of behavioral therapy for urinary symptoms in PD. Based upon the bladder diary-derived UI frequency data (consistent measure used in both behavioral and drug trials), the effect of behavioral therapy and drug therapy to reduce UI frequency is similar^{24,34}. The ICIQ-OAB symptom score range is 0-16, with higher scores indicating worse symptoms. A score ≥ 7 would indicate clinically significant OAB symptoms (urgency, frequency, urgency UI, nocturia) occurring on average at least *sometimes*. In our previous studies, we have observed a 2-3 point reduction in the symptom score, which represents a 12%-19% reduction from baseline^{24,64}. The minimally clinically important difference for the ICIQ-OAB is defined as a statistically significant reduction in the symptom score that is accompanied by a reduction in bother and improvement in OAB-specific QOL. Because the observed reduction (12%-19%) represents a statistically and clinically meaningful difference, we propose a non-inferiority margin of 15%. Thus, we will randomize 90 participants in order to complete the interventions in 80 participants, which assumes 85% power and a non-inferiority margin on the OAB symptom score of 15% at 12-weeks post-randomization.

Sources of Materials: The patients involved in this study will be seen in the Atlanta and Birmingham VAMC/GRECC Continence Clinics and the Philadelphia and Richmond PADRECCs. No tissue, blood, or urine samples will be stored during the study period as part of the protocol. For purposes of this research, baseline and treatment data will be stripped of all patient identifiers and each participant will be given a unique identifier for the study. Patient records will be stored in a locked cabinet in a locked office and will be accessible only to the Principal Investigator, Interventionist, Research Coordinator, Patient Recruiter, Site PI's ([name], [name], and [name]) and co-investigators ([name], [name], [name], [name]). Computer-based records will be maintained through the Veteran's Administration Computerized Patient Record System (CPRS), a secure network with password protection.

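### The power section overstates Table 6: at the planning SD of 2.0, 40 completers per arm meet the table only at margins of 15% and 20%, and at SD 3.0 at none

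*Combined protocol and SAP*

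**What the plan says.** In Power Analysis (Aim 1) the sponsor states that "we will randomize 90 participants in order to complete the interventions in 80 participants", with 85% power and a 15% margin. The Human Subjects section expects about 45 enrolled in each group, so 80 completers means 40 per arm.

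A bolded sentence then says that Table 6 shows "the proposed sample size will permit an assessment of non-inferiority within a range of potential non-inferiority margins that correspond to outcome assessments" in the pilot studies. The table is headed "Margin of Non-Inferiority Between Groups at 12 weeks (Assumes OAB Symptom Score at baseline of = 8.1" and prints:

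| SD at week 12 | 10% | 12.5% | 15% | 20% |
|---|---|---|---|---|
| 1.0 | 23 | 16 | 11 | 7 |
| 2.0 | 89 | 59 | 40 | 24 |
| 3.0 | 198 | 131 | 88 | 52 |

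The pilot outcomes are given in the same section as a fall of 2 to 3 points, "which represents a 12%-19% reduction from baseline". The Human Subjects section links that figure to the margin: "Because the observed reduction (12%-19%) represents a statistically and clinically meaningful difference, we propose a non-inferiority margin of 15" per cent.

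Data Analysis (Primary Outcome for Aim 1) specifies a two-sample t-test on the week-12 score with an SD of 2.0, and adds: "The significance level of the test will be set at an α of 0.025 for a one-sided test of significance".

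**The concern.** The sentence introducing Table 6 is the only statement in the plan about how the primary test stands up to a different margin or a larger SD. It presents the table as evidence of flexibility. At the planning SD, however, the sample meets no tabulated margin stricter than the one already chosen, and it meets that one exactly. One row down, at SD 3.0, it meets none. Someone judging the design from the sentence would credit it with a tolerance that the table does not show.

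**Working it through.** **Inputs.** 40 per arm (80 completers, 1:1), 85% power, margin percentages applied to 8.1, and the table entries, all from Power Analysis. SD 2.0, two-sample t-test and one-sided 0.025 come from Data Analysis. The true difference is taken as 0. That is an assumption: the plan says only that the two treatments have similar effects on incontinence frequency. The table does not label its entries as per arm, but the design cell of 40 agrees with 80 completers only on that reading.

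**Margins in points.** 8.1 × 10%, 12.5%, 15% and 20% = 0.81, 1.0125, 1.215 and 1.62.

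**Step 1: reproduce the table.** By normal approximation, n per arm = 2 × SD² × (z for 1−α + z for 0.85)² / margin².
- One-sided 0.05: (1.645 + 1.036)² = 7.19. At 15% and SD 2.0, 2 × 4 × 7.19 / 1.215² = 39.0. The noncentral t gives 40, as printed.
- All rows by noncentral t at one-sided 0.05: 23/15/11/7, 89/57/40/23 and 198/127/89/51. These are close to the printed values, and all twelve match exactly if the margins are taken as 0.81, 1.0, 1.22 and 1.6 points.
- One-sided 0.025: (1.960 + 1.036)² = 8.98. At 15% and SD 2.0, 2 × 4 × 8.98 / 1.215² = 48.7, so 49 (50 by noncentral t). The table is not reproduced at this level.

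Table 6 therefore corresponds to one-sided 0.05 and 85% power.

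**Step 2: compare with 40 per arm.**
- SD 1.0: all four margins met (largest entry 23).
- SD 2.0: 15% met exactly and 20% met (24); 10% (89) and 12.5% (59) not met.
- SD 3.0: none met (198, 131, 88, 52).

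Six of the twelve cells are out of reach.

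**Step 3: power with 40 per arm.** The noncentrality is margin / (SD × √(2/40)) on 78 degrees of freedom. For 12.5% and SD 2.0 it is 1.0125 / (2 × 0.2236) = 2.264. Against critical values of 1.665 (one-sided 0.05) and 1.991 (one-sided 0.025), power is 72.6% and 60.9%.

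| SD | Margin | Power, one-sided 0.05 | Power, one-sided 0.025 |
|---|---|---|---|
| 2.0 | 10% | 56% | 43% |
| 2.0 | 12.5% | 73% | 61% |
| 2.0 | 15% | 85% | 76.5% |
| 2.0 | 20% | 97% | 95% |
| 3.0 | 10% | 33% | 22% |
| 3.0 | 12.5% | 44% | 32% |
| 3.0 | 15% | 56% | 43% |
| 3.0 | 20% | 77% | 67% |

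At SD 1.0, power at one-sided 0.05 is at least 97% at every margin.

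**Step 4: the edge of the design.** At one-sided 0.05 the smallest margin with 85% power is 14.9% at SD 2.0 and 22.4% at SD 3.0. At a 15% margin the largest SD that keeps 85% power is about 2.01. At one-sided 0.025 the smallest margin at SD 2.0 is 16.8%.

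**Step 5: the two percentage bases.** 2/16 = 12.5% and 3/16 = 18.75%, which fits the stated 12%-19%. On the base of Table 6, 2/8.1 = 24.7% and 3/8.1 = 37.0%. All the table margins (0.81 to 1.62 points) are smaller than the 2-point lower end of the pilot change.

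**The case against.** The strongest defence is that the sentence promises only a range, and the table does support one: 15% to 20% at SD 2.0, and every margin at SD 1.0. The entries above 40 are printed beside the claim, and the margin (15%) and SD (2.0) are fixed in advance, so no planned analysis uses 12.5%. This stands to the extent that the sentence is overstated rather than flatly contradicted, and that the primary analysis itself does not change.

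Four stronger readings are tempting, and the documents do not support them.
- *That 40 per arm is too few at 12.5% without qualification.* At SD 1.0 the table asks for only 16.
- *That the plan claims coverage of 12%-19% and its table refutes this.* The plan never gives 12%-19% as the range of margins. The figure describes the pilot reduction and fits the 16-point scale, so the 12.5% column (1.01 points) is not the lower end of the pilot change (2 points). A 2-point margin with 40 per arm would have over 99% power at SD 2.0 and about 90% at SD 3.0 at one-sided 0.05 (99% and 84% at 0.025).
- *That a failed test is the likely result at a margin near 12.5% or an SD slightly above 2.0.* With equal treatments, success is still the likelier outcome: 73% (61% at 0.025) at 12.5% and SD 2.0, and 70% (57%) at 15% and SD 2.5. Below 50% are, for example, 15% at SD 3.0 and 10% at SD 2.0, both at one-sided 0.025 (43%).
- *That the sample works only for margins of 15% or wider and only for an SD of 2.0 or less.* At one-sided 0.05, 10% at SD 1.0 has 97% power and 20% at SD 2.5 has 89%.

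**Conclusion.** The sentence overstates what Table 6 shows. Half the cells are out of reach, including both margins below 15% at the planning SD and the whole SD 3.0 row, and the design cell is met with nothing to spare. The comparison with the table needs no assumption beyond reading its entries as per arm. The power figures also assume a true difference of 0, 40 completers in each arm and margins taken on 8.1.

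The level matters as well. The table rests on one-sided 0.05 and the primary test is set at 0.025, where even 15% at SD 2.0 gives 76.5% rather than 85%. Any corrected statement must therefore name its alpha. The point concerns a stated property of the design. It does not show that the prespecified margin or test is invalid.

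**What to change.** Replace the sentence introducing Table 6 with text such as:

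> At the planning SD of 2.0, and at the one-sided 0.05 level that reproduces Table 6, 40 per arm gives 85% power only for margins of about 15% of the 8.1 baseline or wider (73% at 12.5%, 56% at 10%). At SD 3.0 it does so for no tabulated margin (56% at 15%, 77% at 20%). At the one-sided 0.025 level specified for the primary test, power at SD 2.0 is about 61% at 12.5%, 76.5% at 15% and 95% at 20%.

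Mark the Table 6 cells above 40, label the entries as per arm, and print the alpha with the table. Add that the table margins are percentages of 8.1, whereas the pilot 12%-19% matches 2 to 3 points on the 16-point scale (25%-37% of 8.1), so the two must not be equated.

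The cost is wording only, with no extra participants. The downside is a less favourable statement of robustness. The new text reports the alpha mismatch but does not resolve it; the sponsor still has to reconcile the level behind Table 6 with the one in Data Analysis.

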The *long term goal* of the PI's research group is to alleviate urinary symptoms as a contributor to disability among Veterans with PD and contribute to understanding of the brain-bladder connection in the setting of neurodegenerative disease. We propose the following specific aims:

Specific Aim #1: Using a RCT, determine non-inferiority of pelvic floor muscle exercise-based behavioral therapy versus drug therapy for urinary symptoms in PD. We hypothesize that pelvic floor muscle exercise-based behavioral therapy will reduce urinary symptom severity with a difference compared to

drug therapy that does not exceed the non-inferiority margin of a validated OAB questionnaire. The primary outcome, OAB severity, will be measured using the OAB symptom questionnaire (International Consultation on Incontinence-OAB (ICIQ-OAB) symptom score) with a non-inferiority margin of 15%.

Specific Aim #2 (mechanistic aim): Determine if domain-specific cognitive function impacts the response to exercise-based behavioral therapy or drug therapy for urinary symptoms.

Aim 2.a. Do higher baseline motor skill learning capacity and executive function scores predict better outcomes in the exercise-based behavioral therapy versus drug therapy group?

Aim 2.b. Compared to exercise therapy, does anticholinergic drug treatment for urinary symptoms worsen executive function and PD motor symptom severity?

Research Design and Methods

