We propose a three-site, RCT conducted at the Atlanta (lead site), Birmingham and Richmond VA medical centers to establish non-inferiority of pelvic floor muscle exercise-based behavioral therapy compared to drug therapy for urinary symptoms in adults with PD. Groups will be stratified by OAB symptom severity, PD motor symptom severity, gender, and site. We will randomize 90 participants in order to complete the study in 80 participants, assuming 85% power and a non-inferiority margin for the OAB symptom score of 15% at 12-weeks. **The primary outcome measure will be urinary symptom severity as measured by the ICIQ-OAB symptom score^{32,33}** collected at 3 time points during the study: baseline, 6 weeks, and 12 weeks. PFME-based behavioral therapy will occur over 3 visits conducted during the first 6 weeks as was performed in the BETTER2 PD study. Participants in the drug therapy group will also have 3 visits during the first 6 weeks in order to individually titrate solifenacin drug therapy according to a validated symptom scale. Solifenacin has been selected because this bladder-selective anticholinergic drug (less risk of cognitive side effects) is the only drug with published evidence of potential efficacy in PD³⁴. At baseline, randomized participants will undergo a brief neuropsychological battery adapted from our current study to assess cognitive factors that may predict a preferred treatment strategy. At the 12-week assessment, the brief neuropsychological battery and MDS-UPDRS will be repeated in order to assess any change associated with treatment allocation. Follow-up visits will occur at weeks 4 and 8 to ascertain side effects and assess treatment adherence.

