Potential subjects may also be referred to the study by their physician either at the host VAMC or academic affiliate. The study will use an approved flyer as advertisement. Potential subjects may contact study staff by phone to determine eligibility or to inquire more about the study. Staff will respond to phone inquiries from patients who self-identify as interested, explain the study, and pre-screen them for eligibility. Those who qualify

preliminarily will be scheduled for a full evaluation and will be mailed an advance copy of the consent form along with a “first appointment letter.” Informed Consent discussion will be conducted during the first visit and if the potential participant consents to participate in the study they will be further evaluated clinically for eligibility based on specific inclusion/exclusion criteria per study protocol.

[figure not shown]
Inclusion criteria:

- Clinical diagnosis of PD determined by a board-certified neurologist with specialty training in movement disorders
- An ICIQ-OAB Symptom Score of ≥ 7 , which indicates clinically significant symptoms of OAB, defined as *presence of urinary urgency with or without urgency incontinence usually with increased daytime frequency and nocturia in the absence of infection or other obvious pathology*^{32,35}.

Exclusion criteria:

- Significant cognitive impairment, as indicated by a Montreal Cognitive Assessment³⁶ (MoCA) score of < 18 (or < 14 for the MoCA Blind), which is the recommended diagnostic cutpoint for dementia in PD³⁷.
- Previous intensive pelvic floor muscle exercise training
- Clinically significant depression as measured by a Geriatric Depression Scale-Short Form³⁸ score ≥ 10 which could affect motivation to fully engage in the intervention
- Use of an indwelling urinary catheter
- Post-void residual (PVR) urine measurement by bladder ultrasound of ≥ 150 mL
- Severe uterine prolapse past the vaginal introitus
- Poorly controlled diabetes defined by a hemoglobin A1c (HgbA1c) of $>9.0\%$ within the last 3 months. Participants with poorly controlled diabetes will be offered enrollment if the OAB symptoms persist after improvement in diabetes control
- Chronic renal failure and on hemodialysis
- Genitourinary cancer with ongoing surgical or external beam radiation treatment
- Previous artificial urinary sphincter, sling procedure or implanted sacral neuromodulation device
- History of bladder-injection of botulinum toxin in the last 12 months

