Randomization: At the second visit, eligible participants will be randomized to one of two groups: treatment with PFME-based behavioral therapy or solifenacin drug therapy. Participants will be stratified by site, gender, UI severity (< or \geq a score of 9 on the ICIQ-OAB), and PD motor symptom severity (MDS-UPDRS < 33 on the part 3 motor score)⁵⁹. Participants will be randomized through computer-generated block randomization in groups of six. Based on preliminary data showing these cut points approximate the means among our randomized participants, we do not anticipate four stratification variables will present a challenge to recruitment. While participants will not be blinded to treatment group, the interventionist will be blinded to the participant's performance on the neuropsychological tests and SRTT performance.

Data Management: Participants' assessment data will be kept in a locked cabinet behind a locked door at each site of the Birmingham/Atlanta GRECC and the Richmond PADRECC. Bladder diaries will be scored by a research assistant who is blinded to the assigned treatment group. Data from the Birmingham and Richmond sites will be uploaded to a secure VA server in the form of PDF documents scanned on a VA device behind the VA firewall. Deidentified data will be entered and verified in Redcap by research staff at the Atlanta site, which will ensure accuracy of the data. A standard form will be used to record the date and reason for all

exclusions and dropouts, and these data will also be entered into the master database. Four times per year the PI will meet with the Atlanta-based data manager to review accrual, data entry, and eligibility criteria and examine the database for outliers or database entry errors at each site. The Redcap database will then be converted and data analyses will be completed in SAS 9.4 (SAS Institute, Cary, NC). Additional details regarding confidentiality of patient data are included in the Human Subjects plan.

Specific Aim #1: Using a RCT, determine non-inferiority of pelvic floor muscle exercise-based behavioral therapy versus drug therapy for urinary symptoms in PD.

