To assess the potential impact on motor symptoms, we will assess the change in the motor symptom subscale of the MDS-UPDRS (part 3 score). Similar to the cognitive testing, baseline and 12-week post-randomization assessments will be evaluated using paired t-tests to assess for change within the drug group and two-sample t-tests for difference across groups, with the behavioral therapy group serving as a control for this analysis. Previous research suggests an increase in the MDS-UPDRS part 3 score of 4.6 points is associated with clinically relevant decline in motor function⁷⁰.

Visit Schedule

Visit 1: Baseline (One phone/telehealth session and one in-person session)

Explanation of study procedures and consent to be a participant

Interview: Demographics, continence and medical history, MoCA, LSA, GDS

Physical: Height, weight, vital signs, cardiac, pulmonary, and abdominal exam, genital and rectal exam, basic neurologic exam, MDS-UPDRS, determination of post-void residual by bladder ultrasound

Laboratory Examination: Urinalysis and BMP and HgbA1c if indicated

Education: How to complete bladder diary, handout take-home questionnaires (ICIQ-OAB and OAB-QOL)

Visit 2 (Part 1) : Randomization

Interview: Collect and review 7-day bladder diary, ICIQ questionnaires

Physical: Vital signs; review laboratory results; determination of post-void residual by bladder ultrasound if not conducted at first visit;

Procedure: **Randomization (Behavioral Therapy or Drug Therapy)**

Behavioral Therapy	Drug Therapy

Visit 2 (Part 2): Behavioral Therapy Randomization
 
Procedure: Neuropsychological battery, SRTT, Pelvic floor muscle exercise training
 
Education: specific behavioral techniques for constipation, modification of fluid intake or timed voiding
	
Visit 2 (Part 2) : Drug Therapy Randomization
 
Procedure: Neuropsychological battery, SRTT
 
Education: Medication

Visit 3: Behavioral Therapy (2 weeks)
 
Interview: Review PFME record, address new problems, reinforce practice at home and verbal feedback regarding muscle control
 
Education: Urge suppression strategy, management of stress-related urine loss (if applicable)
	
Visit 3: Drug Therapy (2 weeks)
 
Interview: Medication Management, Medication Side Effects
 
Education: Medication & Bladder Diary & Forms (to return at Visit 5)

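### The first Aim 1 analysis treats each arm's fall from a baseline screened at 7 or more as a treatment effect, and its model uses baseline both as an outcome and as a covariate

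*Combined protocol and SAP*

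**What the plan says.** Data Analysis, Primary Outcome for Aim 1, sets out two steps. The first has the stated purpose "To evaluate the impact of treatment within group" and uses a "random effects mixed model with adjustment for baseline OAB symptom severity to compare mean ICIQ-OAB symptom scores across the three time points". The second is a two-sample t-test of the arms' week-12 means against the non-inferiority margin, at one-sided 0.025.

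Other sections fix the meaning of the first step:

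- Research Design and Methods says the ICIQ-OAB is "collected at 3 time points during the study: baseline, 6 weeks, and 12 weeks". Baseline is therefore one of the three outcome time points.
- Specific Aim #1 identifies severity with the same instrument: "The primary outcome, OAB severity, will be measured using the OAB symptom questionnaire". The severity stratum under Randomization is also a cut on it, at "a score of 9 on the ICIQ-OAB".
- The inclusion criteria require "An ICIQ-OAB Symptom Score of ≥ 7", "which indicates clinically significant symptoms of OAB".
- The Visit Schedule hands out the ICIQ-OAB at Visit 1 for completion at home. Enrollment and Neuropsychological Assessment has staff review the completed questionnaires at Visit 2 to decide eligibility. No further pre-treatment ICIQ-OAB is described, so the screening score is the baseline.
- Both arms receive active treatment.

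**The concern.** There are two separate problems.

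**Interpretation.** People admitted because a fluctuating score was high on one occasion will, on average, score lower next time even if nothing is done. Attention, diary keeping and natural course also act on both arms. A within-arm change from baseline cannot separate these from treatment, yet the plan names the change as the impact of treatment. A report could then state that each therapy significantly reduced symptoms when part of the fall comes from selection.

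**Specification.** Adjusting for a variable that is also one of the responses makes the model explain baseline by itself. With the continuous score, the baseline rows pull the common slope toward 1. Their very small residuals are pooled with those at weeks 6 and 12, so the model understates the spread at follow-up. This would matter if arm differences or adjusted means were read off the same fit.

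**Working it through.** **The plan's own figures.** The plan gives no number for this model; its 40 completers per arm belong to the t-test. The benchmark is the pilot fall in Power Analysis: 2 to 3 points, described as 12 to 19% from baseline. Those percentages are reproduced on the 16-point range (2/16 = 12.5%, 3/16 = 18.75%). On the assumed baseline of 8.1 they would be 24.7% and 37.0%. The comparison below is therefore in points.

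**Regression to the mean.** Inputs from the documents are the entry cut of 7, the assumed baseline mean of 8.1 and, as a guide to spread, the SD of 2.0. Assumed, because the documents give neither: the unscreened population mean and the retest correlation ρ. For a normal population with mean μ, screened at 7:

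expected fall with no treatment effect = (1 − ρ) × (mean of those admitted − μ)

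| μ, SD | Mean admitted | Excess | ρ = 0.5 | ρ = 0.7 | ρ = 0.9 |
|---|---|---|---|---|---|
| 8, 2 | 9.02 | 1.02 | 0.51 | 0.31 | 0.10 |
| 7, 2 | 8.60 | 1.60 | 0.80 | 0.48 | 0.16 |
| 5.24, 2 (solved to give 8.1) | 8.10 | 2.86 | 1.43 | 0.86 | 0.29 |

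The range is thus about 0.1 to 1.4 points. A wider population goes slightly beyond it: for mean 6, SD 3 the admitted mean is 9.06, so at ρ = 0.5 the fall is 0.5 × 3.06 = 1.53.

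**False within-arm findings.** Arms of 40 with no treatment effect were simulated 200 times per setting and fitted with a random intercept at the three visits. The table shows how often the week-12 versus baseline contrast was significant at two-sided 0.05.

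| Setting (SD 2) | Mean change | Without covariate | With covariate |
|---|---|---|---|
| μ 7, ρ 0.7, screened | −0.49 | 56% | 55% |
| μ 7, ρ 0.8, screened | −0.31 to −0.30 | 36% | 31% |
| μ 6, ρ 0.7, screened | −0.68 to −0.65 | 83% | 80% |
| μ 8, ρ 0.7, no screen | 0.00 to −0.01 | 4% | 3% |

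The screen produces the false findings, and the covariate does not remove them. In the first setting, adding the covariate cut the estimated random-intercept variance from 1.25 to 0.27, which shows the distorted covariance model.

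**Arm contrast from the same model.** The simulation had 45 per arm, about 11% missing at week 12 and a continuous covariate, with correlation of baseline with follow-up 0.3 or 0.5 and baseline screened or not. Model SE over the empirical SD of the week-12 arm difference, in the four settings:

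- 0.359/0.430 = 0.83
- 0.378/0.460 = 0.82
- 0.321/0.371 = 0.87
- 0.330/0.413 = 0.80

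The SE is therefore 13 to 20% too small, and 95% intervals covered 89 to 92%. A second set of runs (population mean 7, SD 2, correlations 0.3 to 0.7) gave 11 to 26% and coverage of 85 to 92%, against 92 to 97% for week-12 ANCOVA on the same data.

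**How much is due to the covariate.** With screening and correlations of 0.3 and 0.5, SE/SD was 0.86 and 0.78 with the covariate, and 0.90 and 0.88 without it. Part of the shortfall therefore comes from the random-intercept assumption of equal variance at every visit, which screening violates by compressing baseline.

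**Non-inferiority comparison.** With no effect, μ 7, SD 2, ρ 0.7 and the same screen, the week-12 difference between arms averaged 0.00 over 4,000 runs, while the within-arm change averaged −0.49.

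**The case against.** The best defence is that this step is preliminary. The plan uses the mixed model only within group and compares the arms by a separate t-test, so the standard-error and coverage figures describe an estimate that the plan does not take. That stands. For the contrast it does take, the SE of the week-12 change was 0.313 with the covariate and 0.314 without at correlation 0.3, and 0.283 and 0.284 at 0.5.

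Three further points also stand. The plan does not say whether baseline severity means the continuous score or the stratum cut at 9. With the stratum, the baseline residuals are not near zero, and in unscreened runs the shortfall was only 5 to 7%. Part of the shortfall is due to the equal-variance assumption. The size of the regression effect rests wholly on assumed inputs.

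A reader might infer more than the documents support:

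- *That the non-inferiority conclusion is biased.* It is not. Both randomized arms pass the same screen, so the effect cancels in their difference.
- *That within-arm falls would be the only sign that either treatment works.* The plan also has diary, bother, quality-of-life, benefit and satisfaction outcomes, and it cites a randomized pilot of solifenacin in PD. Uncontrolled changes in those outcomes carry a similar caution, but they are further evidence.
- *That most of the pilots' 2 to 3 points was artefact.* The documents give neither the pilots' score distributions nor a retest correlation, so this cannot be shown.

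None of this rescues the label. The plan still attributes an uncontrolled change from a screened score to treatment.

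**Conclusion.** The concern holds for the first Aim 1 analysis and stops there. Calling the within-arm change the impact of treatment is unsupported, because the change includes a selection effect that the model cannot remove. Its size is about 0.1 to 1.4 points for roughly normal scores, population means of about 5 to 8, SD 2 and retest correlations of 0.5 to 0.9. That runs from negligible to 70% of a 2-point fall (1.4/2), and it is enough to make a null within-arm test significant in roughly a third to four fifths of the simulated arms of 40.

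The model is also mis-specified under either reading of baseline severity, since the baseline score is an outcome as well. The consequence is conditional: standard errors roughly 10 to 25% too small, only if arm contrasts or adjusted means are drawn from a random-intercept fit with the continuous covariate, and only partly because of that covariate. The non-inferiority t-test is not biased by either problem. This should be corrected before analysis, but it does not threaten the primary conclusion.

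**What to change.** In Primary Outcome for Aim 1:

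1. Delete the purpose clause "To evaluate the impact of treatment within group" and label within-arm change from baseline as descriptive, with a sentence saying that it includes regression to the mean, natural course and non-specific effects.
2. Use weeks 6 and 12 as the responses, with baseline ICIQ-OAB score as a continuous covariate with a visit-specific slope, plus arm, visit, arm-by-visit and an unstructured covariance. An acceptable alternative keeps all three visits as responses, drops the baseline covariate, constrains the arms to be equal at baseline and uses an unstructured covariance. The covariance must be named: under a random intercept this alternative still gave SE/SD of 0.89 and 0.84 and coverage of 92% and 90%.
3. Report the arm contrasts from this model as supportive, and state that the specified non-inferiority test governs.

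The cost is SAP wording and a changed model statement in SAS. Visits, data collection, margin and sample size are unaffected. The one small downside is a second week-12 between-arm estimate beside the t-test, which is why the third item is needed.
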